Protocol deviation is defined as any divergence from what was pre-planned and approved by the institutional review board. As the study is conducted as part of routine care and operations, there are practical constraints that may cause protocol deviations to occur. Rescheduling of appointments by the parents (e.g. due to work constraints, child's sickness, other events) or defaulting appointments is inevitable. Hence, for per-protocol analyses, we will only exclude participants with major protocol deviation, which will be defined as participants who do not complete 80% of the intended therapy sessions allocated for their study arm. This means that a control arm participant must attend at least 8 out of 10 clinic-based sessions. For the remaining 2 sessions, participants can either be attending it through video-conferencing (due to the COVID-19 pandemic) or miss the appointment.

Quantitative Outcomes

For the randomized trial, since the study is a non-inferiority study, statistical analysis will be carried out on a per-protocol basis. Subjects with any major protocol deviation as defined above will be excluded from the final analysis.

All demographic, clinical and cost characteristics will be analysed descriptively. Mean (SD) or median (range), whichever is more appropriate will be reported for numerical variables, while N (%) will be reported for categorical variables. 2-sample t-tests, or Mann-Whitney U tests will be used to compare the change of MSEL score between 2 arms. Mean difference and 95% CI will be estimated. If the lower boundary of the 95% CI is more than -5, non-inferiority will be declared. Changes in the quality of parent-child engagement, parental stress index score, and adaptive score will be compared by using either a 2-sample t-test, or a Mann-Whitney U test, whichever is more appropriate. Linear regression will be used to adjust for any covariates.

Cost-Effectiveness Analysis

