To examine cost-effectiveness, we will compare resource utilization between treatment and control groups to estimate resource and cost differences in absolute terms from the direct medical cost perspective as well as the societal perspective (inclusive of the direct costs of travel and the indirect cost of parental time). As the trial focuses on non-inferiority, the assessment of cost-effectiveness will rely on whether the intervention is cost-saving relative to the standard of care. We will also perform modelling estimates to quantify the uncertainty surrounding the incremental cost-effectiveness ratio.

Methodology

Decision Problem

Objective

To assess the cost-effectiveness, in terms of incremental cost effectiveness ratio (ICER) of the **tele-health (telerehab) mode** of delivering the early intervention (EI) in children with

Autism Spectrum Disorder (ASD) relative to the **standard care** (clinic-based sessions only) in costs and outcomes as measured by Mullen Scales of Early Learning (MSEL), Vineland Adaptive Behavioural Composite score (VABS) and Joint Engagement Rating Inventory (JERI).

$$ICER = \frac{Costs_{New} - Costs_{Old}}{Effects_{New} - Effects_{Old}}$$

Figure 1: Incremental cost-effectiveness ratio (ICER), calculated by the difference in cost between two possible interventions, divided by the difference in their effect.

Target Population

The study target population for these analyses will be the children assessed to fulfil the inclusion criteria of the Telerehab RCT from NUH CDU. The delivery of early intervention heavily involves a caregiver, often the biological parent(s) of the children receiving therapy for early intervention.

Study Perspective

The study will take on a **societal perspective**. This includes healthcare costs from the provider’s perspective, non-healthcare costs incurred by the patient from social care and child care, as well as productivity losses for the patient’s caregiver.

The time horizon of the study includes the cost incurred and benefits from the entire program duration, from enrolment to the final review.

Comparator – Standard Care

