The comparator for this study will be the standard model of delivery for EI which are clinic-based (face-to-face) sessions with the patients and their primary caregiver. The **variable treatment component** between telerehab and the standard model of delivery is the number of video-conferencing vs clinic-based intervention sessions. The assumption is that all non-therapy related costs such as paediatrician reviews will be the same for subjects in both study arms.

Table 1: Variable components of care between standard and telerehab care model

	Standard Model	Telerehab Model
Clinic-based intervention (45mins + 15mins)	16 sessions	2 sessions
Video-conferencing (30mins + 15mins)	0 sessions	16 sessions
Total Therapy time	720mins + 240 mins (admin)	570mins + 270 mins (admin)

Analysis Approach

We will take on two approaches to calculate the ICER. First, is the use of patient-level data for cost-effectiveness analysis. Second, we will use estimates generated from analyses Monte Carlo simulation to estimate the cost-effectiveness through parameters (mean, standard errors) obtained from the study. This will be decided by the analyst with the justification for the approach documented.

Time Horizon

The time horizon considered will be the duration of the program (around 1 year), from enrolment till final review. The cost and outcomes data collected will be limited to the duration of the program. It will be hard to justify extrapolations and assumptions after the program after the patient has transited out of NUH CDU to EIPIC, where treatment frequency and intensity will be substantially variable.

Univariate sensitivity analysis

One-way sensitivity analysis will be performed to assess the impact of a change in parameters.

Probabilistic sensitivity analysis²

Probabilistic sensitivity analysis (PSA) will be performed by incorporating the degree of uncertainty for each parameter. This involves assigning a primary mean value for each model parameter (mean cost, number of visits, probabilities) and the distribution of possible values. Monte Carlo simulation was used to estimate mean expected costs and outcomes, and statistical measures of expected variance (SD) around the mean for 1,000 iterations drawn from the distributions defined.

Direct Healthcare Costs

Health sector cost

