We will examine the primary outcome, Mullen's Scale of Early Learning (MSEL) Early Learning Composite Score (ELC) as the key outcome of interest (i.e. the denominator for ICER). We will also examine the outcomes in VABS and JERI as outcomes of interest. Parameters for modelling for outcomes will be obtained from analyses specified in the previous section.

Input Data for Outcomes and Cost Data for the Model

The input data for the model from the survey administered is listed below in Table 2.

Table 2: Data Source and Parameters Estimates and Distribution for Cost-effectiveness Analysis

	Standard	Telerehab	Parameters Estimated	Distribution
Outcomes	Estimates from analysis from t-test/regression for: MSEL-ELC, VABS composite score and/or JERI	Estimates from analysis from t-test/regression for: MSEL-ELC, VABS composite score and/or JERI	Mean (SD) improvement in outcomes examined	Normal
Direct Healthcare Cost				
Attendance for therapy sessions	Number of clinic-based therapy sessions attended	Number of clinic-based and telerehab therapy sessions attended Telerehab consists of clinic-based sessions at the start of the program + telerehab sessions	Mean (SD) of therapy session attended across each study arm	Normal or gamma
Healthcare cost	Total cost of clinic-based therapy sessions	Total cost of clinic-based + telerehab therapy sessions	Number of visits * fixed cost per visit (standardized for FY2021/22)	Fixed
Direct Non-healthcare Cost				
Transport costs	Survey questions 
 • What mode of transport did you use to get here today? • How much did it cost? • Do you usually use this mode of transport to get to the clinic/CDU? • If no, what is your usual mode of transport? • How much did it cost? 	Survey question 
 • What mode of transport did you use to get here today? • How much did it cost? • Do you usually use this mode of transport to get to the clinic/CDU? • If no, what is your usual mode of transport? • How much did it cost? 	The total transportation cost incurred by participants will differ between study arms by nature of the mode of delivery. The actual transportation cost will account for two-way (round trip) and the observed visits (accounting for missed appointments for example)	Normal

			Transport Cost = Total no. of trips * Mean transport cost * 2	

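### Cost-saving is the stated criterion for cost-effectiveness, but the plan does not make it conditional on non-inferiority being declared

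*Combined protocol and SAP*

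**What the plan says.** All references are to the combined protocol and SAP.

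- **Criterion.** Under Cost-Effectiveness Analysis, "the assessment of cost-effectiveness will rely on whether the intervention is cost-saving relative to the standard of care". The sentence opens with its reason: "As the trial focuses on non-inferiority, the assessment of cost-effectiveness". Under Evaluation Questions, the cost-effectiveness question likewise puts cost-saving in brackets as the meaning of cost-effective.
- **Non-inferiority rule.** Under Quantitative Outcomes: "If the lower boundary of the 95% CI is more than -5, non-inferiority will be declared". That section does not mention the economic conclusion, and the economic section does not mention the -5 limit.
- **Other economic analyses.** The next sentence of Cost-Effectiveness Analysis adds: "We will also perform modelling estimates to quantify the uncertainty surrounding the incremental cost-effectiveness ratio". The Objective is framed in terms of the ICER, with MSEL, VABS and JERI as effects. Analysis Approach says "We will take on two approaches to calculate the ICER", and one-way and probabilistic sensitivity analyses follow. The Outcomes section makes the MSEL Early Learning Composite the ICER denominator. No willingness-to-pay threshold or decision rule for the ICER appears anywhere.

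**The concern.** Reducing a cost-effectiveness question to a cost comparison is sound once the effects have been shown to be acceptably close. The plan makes that reduction because of how the trial is designed, before the result is known. It does not say what will be concluded if telerehab is cheaper but the confidence interval for the MSEL difference extends below -5.

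At stake is the answer to evaluation question g, whether telerehab is more cost-effective than standard care. As the text stands, a favourable economic conclusion could be reported beside an inconclusive or failed primary analysis, without departing from the plan. The dissemination plan sends reports to the program's management and health ministry stakeholders, so the wording of that conclusion should be settled beforehand.

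**Working it through.** **1. Reproduce the plan's sample size.** Inputs from Sample Size Calculation: margin 5, SD of change 15, expected difference +1.5 in favour of telerehab, one-sided 5%, power 80%.

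n per arm = 2 × SD² × (z(0.95) + z(0.80))² / (margin + difference)² = 2 × 225 × (1.645 + 0.842)² / 6.5² = 65.9 (using unrounded z values), rounded up to 66. The total is 132, which matches the plan.

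**2. How often is non-inferiority not declared?** For a true difference d (telerehab minus standard) and n per arm:

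SE = 15 × √(2/n), which is 2.611 at n = 66 and 2.121 at n = 100

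P(not declared) = 1 − Φ((5 + d)/SE − z)

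Here z = 1.645 for the one-sided 5% test used in sizing. For the lower limit of a two-sided 95% interval, as written in Quantitative Outcomes, z = 1.960.

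Worked case, d = +1.5 and n = 66: 6.5/2.611 = 2.489.
- One-sided 5%: 1 − Φ(2.489 − 1.645) = 1 − 0.801 = 19.9%.
- 95% interval: 1 − Φ(2.489 − 1.960) = 1 − 0.702 = 29.8%.

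| n per arm | True difference | One-sided 5% | 95% interval rule |
|---|---|---|---|
| 66 | +1.5 (plan) | 19.9% | 29.8% |
| 66 | 0 (assumed) | 39.4% | 51.8% |
| 66 | -5 (assumed) | 95.0% | 97.5% |
| 100 | +1.5 (plan) | 7.8% | 13.5% |
| 100 | 0 (assumed) | 23.8% | 34.6% |
| 100 | -5 (assumed) | 95.0% | 97.5% |

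The rows with 66 per arm use the number the plan calls sufficient. Those with 100 per arm assume that everyone recruited is analysed. With the t distribution in place of the normal, the two figures in the first row become 20.3% and 30.5%.

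**3. Does the ICER settle the failed case?** The ICER is the cost difference divided by the effect difference. With illustrative values:
- saving 100 and losing 6 points: (-100)/(-6) = 16.7 per point;
- spending 100 more and gaining 6 points: 100/6 = 16.7 per point.

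The same number describes opposite situations, so without a decision rule it does not say whether a cheaper program is acceptable. The probabilistic analysis is described as giving mean costs and outcomes with their SDs. No joint decision measure is named.

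**4. Is telerehab bound to be cheaper?** Table 1 gives 16 clinic sessions for standard care, and 2 clinic plus 16 video sessions (18 in all) for telerehab. Scheduled minutes fall from 720 + 240 = 960 to 570 + 270 = 840. Table 2, however, costs therapy as visits times a fixed charge per visit. With clinic charge c and video charge v, full attendance saves money in this component only if

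2c + 16v < 16c, that is v < 14c/16 = 0.875c.

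No charges are given. If the charges were equal, telerehab would cost 18/16 = 1.125 times as much, or 12.5% more. Less travel favours telerehab. Against that, the indicator table counts development and platform costs, and Table 2 counts paid care, employment changes and parental time, whose direction between arms is unknown.

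**The case against.** The strongest reply is that effects are not ignored. The ICER objective, the modelling of its uncertainty, the two ICER approaches and the sensitivity analyses all bring MSEL into the economic results, so a shortfall on MSEL would show there. A reader might infer from the criterion sentence that cost is the only thing examined. The documents do not support that. What remains is that those analyses have no rule for reaching a conclusion, while the criterion sentence does state one.

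Second, the opening clause of that sentence can be read as presupposing that non-inferiority has been shown. This is fair. The plan states no conclusion for the failed case, so one cannot say that a cheaper program that missed the margin would be called cost-effective, only that it could be. The two possible readings are themselves a reason to clarify.

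Third, a reader might infer from Table 1 that savings are almost guaranteed by the design. Step 4 of the working shows why this does not follow.

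Fourth, the 20% and 30% do not measure wrong conclusions, and that objection stands in full. At true differences of +1.5 or 0, a cheaper telerehab program really would be as good or better, so calling it cost-effective would be correct even if the trial were inconclusive. The 20% is simply the complement of the stated 80% power. The rise to 30% comes from a separate mismatch between the one-sided 5% used for sizing and the 95% interval used for the decision.

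**Conclusion.** The concern holds in a limited form. Cost-saving is the stated criterion for cost-effectiveness and is not tied to a declared non-inferiority result. The accompanying ICER work has no decision rule and an ambiguous sign, so the text leaves room to call a cheaper program cost-effective after it misses the -5 margin.

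The unaddressed case is not remote. It arises in about 20% of trials (one-sided 5%) or 30% (95% interval rule) with a true difference of +1.5, SD 15 and 66 per arm. With all 100 per arm analysed, the 95% interval rule gives 13.5%. If the arms are truly equal, which is an assumption made here, it gives 34.6% to 51.8%, depending on the number analysed. These figures are not probabilities of a false claim. The gap has consequences only if telerehab is also cheaper, and the documents give no charges from which to judge that.

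This affects a secondary conclusion. The primary test and the sample size are untouched. It is worth correcting because the correction is cheap and changes what the trial may claim.

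**What to change.** In Cost-Effectiveness Analysis, replace the criterion sentence with wording to this effect:

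*Cost-saving will be the criterion for cost-effectiveness only if non-inferiority on the primary MSEL score has been declared. If it has not been declared, incremental cost and incremental effect will be reported jointly with their uncertainty, on a cost-effectiveness plane or as net benefit over a range of thresholds, and no cost-effectiveness claim will be made from cost alone.*

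The bracketed equation of cost-effective with cost-saving under Evaluation Questions should carry the same condition. No significance requirement on the cost difference is needed to close this gap.

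The change takes a few sentences. It needs no new data and no change in sample size, and the joint reporting draws on the patient-level and simulation work already planned. The downside is that a cost-effectiveness claim based on savings is no longer available when the primary analysis fails.

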Visit 5b: For the telerehab group, initial assessments and observations will be collected through 2 settings, one clinic-based, as well as one using VC. The latter is done in order to observe parent-child interactions and skills demonstrated by the child in the context of the natural home environment. The VC assessment and intervention will be conducted using a MOHH commissioned VC platform. This platform will allow the therapist and parents to see, hear, and communicate with one another live in real-time. The therapist will access the program from an office computer with a web-camera in the clinic, whereas parents will access the program from their home. Parents who do not have the necessary equipment for VC will be provided with notebook computers and needed accessories. An orientation to the use and care of VC equipment will be provided.

Visit 6: Parents of children in both programs will attend a parent education workshop. The workshop will discuss the role of parents and therapists in early intervention, the key areas that children have difficulties with during development, the use of routines to facilitate the child's learning and strategies that can be embedded in routines. If parents choose to not attend the workshop or are unable to attend their scheduled workshop, parents can still proceed with the intervention phase. Parents who are unable to attend the workshop will be reminded to reschedule the workshop to the next available date and will have training slides and materials sent to them through email for their reading. Parents will have also have opportunities to seek further clarification during subsequent visits with their therapist.

Intervention: Standard Program

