At the start of the session, the parents' progress from the past topic and any other updates will be reviewed and discussed for 5–10 minutes. This is then followed by a 10-minute parent-child play activity. The activity allows the therapist to observe the parent's competency in implementing intervention (i.e. the goals and effective use of strategies) from the previous session's coaching. Based on observations made, the therapist will coach further to strengthen parent's confidence and competency in using strategies to facilitate the attainment of specific learning objectives in the IIP. During the final 10–15 minutes of each session, the therapist will seek feedback from the parent to understand parent's clarity, comfort and confidence in implementing the intervention plan and provide further input and information if required. The therapist will also address any challenges faced or anticipated in the context of implementing the intervention in the home context. The therapist will discuss with parents to implement the intervention plan using at least two play or daily routines (naturally occurring opportunities) identified by the parent. Adult learning principles will be adopted by

the therapist to facilitate active participation in planning and intervention implementation. For clinic-based sessions, an additional 15 minutes is allocated to allow the child and parents to settle down and transit into and out of the therapist's room.

Data collection: For all subjects, video recordings of parent child interactions will be taken at 4 specific time points, namely Baseline, two Midterm reviews and Final review. Specific to the children in the telerehab arm, an additional video recording of parent-child interaction will be done through VC for each on-site review session, totalling 8 video recording time points throughout the program's duration. Recorded videos will be downloaded and transferred to a password encrypted hard drive authorized by the institution data protection and security teams. These recordings can only be accessed by authorized team members with institutional accounts and external raters. They will be used for evaluation on the JERI, NDBI-Fi and for inter-rater reliability assessment.

Parent-delivered therapy (Home-based)

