Health sector cost will be primarily attributed to the cost of treatment delivered by the institution, NUH CDU. The gross charges for paediatrician review, IIP review and administering surveys and assessments for the children are consistent in both study arms. Only variable cost between both study arms will be included. The variable cost includes the clinic-based intervention charges and video-conferencing-based intervention charges across both arms. The assumption for health sector cost will be that participants from both arms attend all the review and assessment sessions as they are essential to the intervention plan. The only variability would be attributed to defaulted therapy sessions.

Direct Non-Healthcare Costs

Transportation Costs

Transportation cost will be estimated using the responses from the baseline cost survey administered to caregivers. The total transport cost per study arm (standard vs telerehab) will be calculated by multiplying the *observed number of clinic-based visits* (accounting for missed appointments/therapy sessions) with the average cost of transportation indicated by the caregiver multiplied by two to account for round-trip travelling.

Caregiver and other care costs

Costs from other sectors include care cost from attending courses, hiring domestic helpers and/or other forms of care support for the child. This information is obtained from the cost survey administered to the parents.

Indirect Costs

Productivity Loss

Productivity loss will be calculated using the human capital approach. The human-capital method takes the patient's perspective (in this case the parent's time) and counts any hour not worked as an hour lost.

² <https://yhec.co.uk/glossary/probabilistic-stochastic-sensitivity-analysis/>
TRAutism HSDP Protocol_Version 8_19/08/2022

Productivity loss in this study will be primarily attributed to the caregiver taking time off from work to attend treatment with the patient (their child) and applying intervention strategies with the child. The time spent by caregivers includes the following:

- i. time spent on travelling CDU for treatment (two-way trip);
- ii. time spent on therapy sessions (30mins for video-conference, 45mins for clinic-based);
- iii. employment charges

Outcomes

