Annex 1: Program schedule

Visit no.	Standard program		Telerehabilitation program	
	Test/Intervention	Time (min)	Test/Intervention	Time (min)
ASSESSMENT PHASE				
Visit 0	First Paediatrician visit Screening for ASD (DSM-5) Initiate informed consent taking for study (refer to consent form) – can be done at Visit 0 or 1			30
Visit 1	Second Paediatrician visit Initiate informed consent taking for study (refer to consent form) – can be done at Visit 0 or 1 Refer for ADOS and MSEL if consent is given Otherwise continue with standard care			30
Visit 2-3	Nurse Assessment MSEL + PSI			120
	Psychologist Assessment ADOS + VABS			120
Visit 4	Third Paediatrician visit Paediatrician visit to share Mullen's & ADOS-2 report and confirm enrolment into the study and to inform arm of study. If patient does not meet the inclusion criteria. They will be referred to standard care outside the trial.			30

Visit 5	Therapist Assessment (clinic based)			90
	
 • Foundational Skills Curriculum (FSC) assessment • Parent interview on routines • Joint engagement rating inventory (JERI) • Family Early Intervention Quality of life survey (FEIQoL) • Demographic survey • Cost Survey 			
			Preparation for video conferencing Video conferencing observation (FSC, NDBI-Fi)	30
Visit 6	Parent Education Workshop (Can be conducted either in person or through electronic training slides)			90
For eligible and chosen participants, pre-interview will be conducted between visit 5 and before the Intervention Phase.				45
INTERVENTION PHASE				
1 st block of intervention	Clinic-based intervention (CBI) x 6 (Commencement of Individualised intervention plan (IIP))	60 x 6	Clinic-based intervention (CBI) x 2 (Commencement of Individualised intervention plan (IIP))	60 x 2
			Video conference-based intervention (VCBI) x 4	45 x 4
Parent-delivered therapy home-based)				
2 nd block of intervention	Clinic-based intervention (CBI) x 4	60 x 4	Video conference-based intervention (VCBI) x 4	45 x 4

Visit 7-8	Fourth Paediatrician visit Midpoint Review by paediatrician (clinic based or teleconsultation)			30
	
 • Child's profile, progress • Child and Family's needs • Appropriate recommendations and referrals (if needed) 			
	Midterm Progress Review with Therapist (clinic based)			60
	
 • Foundational skills curriculum – Child's development profile • Joint Engagement Rating Inventory (JERI) • Cost Survey 			

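### The costing assumes equal non-therapy costs in the two arms, but Annex 1 schedules two 30-minute video observations for telerehab only

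*Combined protocol and SAP*

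**What the plan says.** Under Comparator – Standard Care, the plan treats the number of clinic and VC intervention sessions as the only component that varies between arms, and assumes that "all non-therapy related costs such as paediatrician reviews will be the same for subjects in both study arms". The Health sector cost paragraph extends this to assessments: charges for "administering surveys and assessments for the children are consistent in both study arms", and "Only variable cost between both study arms will be included". The variable costs it then names are the charges for clinic and VC intervention sessions.

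Table 1 sets out those sessions: "Clinic-based intervention (45mins + 15mins)" at 16 for standard and 2 for telerehab, and "Video-conferencing (30mins + 15mins)" at 0 and 16.

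The schedule differs. In Annex 1 the telerehab column alone carries "Video conferencing observation (FSC, NDBI-Fi)" twice, at Visit 5 (in one entry with VC preparation) and at Visits 12-14, with 30 min each time. The descriptions of Visit 5b and of the final therapist review confirm that both come on top of the clinic assessment. Visit 5b also states: "An orientation to the use and care of VC equipment will be provided". The Data collection paragraph for the telerehab program goes further: for that arm, "an additional video recording of parent-child interaction will be done through VC for each on-site review session", giving 8 recording points against 4 in the standard arm.

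**The concern.** An assumption of no difference is safe only where the two columns of the schedule match. Here they do not, and every unmatched item lies in the telerehab arm. Leaving these items out therefore makes telerehab look cheaper and quicker than it is.

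This bears on stated aims. Program Implementation lists less time and resource use per completed course as a service objective, and the Cost-Effectiveness Analysis section rests its conclusion on whether telerehab saves cost. The contacts missing from Table 1 are also missing from the telerehab visit count, and from the caregiver time under Productivity Loss, which counts therapy sessions and travel.

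**Working it through.** **Inputs**
- Table 1: clinic session 45 + 15 min; VC session 30 + 15 min; 16 clinic sessions (standard); 2 clinic and 16 VC sessions (telerehab).
- Annex 1: sessions by block, and two telerehab-only VC observations of 30 min each.
- Data collection paragraph: 8 − 4 = 4 extra VC recordings for telerehab, of which two fall at the midterm reviews. No duration is given, and the midterm ones are not in Annex 1.

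**Step 1: reproduce Table 1**
- Standard: 16 × 45 = 720 and 16 × 15 = 240; total 960 min.
- Telerehab: 2 × 45 + 16 × 30 = 570 and 18 × 15 = 270; total 840 min.
- Check against Annex 1: (6 + 4 + 6) × 60 = 960; 2 × 60 + (4 + 4 + 2 + 6) × 45 = 840.

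Table 1 is correct for what it counts.

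**Step 2: implied difference**

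960 − 840 = 120 min per child, made up of 150 min less therapy (720 − 570) and 30 min more administration (270 − 240). The plan does not state the 120 min; it follows by subtraction.

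**Step 3: add the telerehab-only contacts**

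Remaining difference = 120 − extra minutes; share removed = extra / 120.

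| Counted as programme activity | Extra min | Difference left | Share removed |
|---|---|---|---|
| Neither observation | 0 | 120 | 0% |
| Baseline observation only | 30 | 90 | 25% |
| Both Annex 1 observations | 2 × 30 = 60 | 60 | 50% |
| Both, plus midterm recordings at an assumed 10 min each | 60 + 20 = 80 | 40 | 67% |
| Both, plus midterm at an assumed 15 min each | 60 + 30 = 90 | 30 | 75% |
| Both, plus midterm at an assumed 20 min each | 60 + 40 = 100 | 20 | 83% |
| Both, plus midterm at an assumed 30 min each | 60 + 60 = 120 | 0 | 100% |

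The first three rows use only durations in the documents. The last four rest on an assumed duration. Against the 150-min therapy difference without administration, the two observations are 60/150 = 40%.

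**Step 4: how this reaches the costs**

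Table 2 computes healthcare cost as visits times a fixed charge, so Table 1 minutes do not enter it. The contacts would enter as visits: telerehab has 2 + 16 = 18 counted sessions, against 19 with the baseline observation and 20 with both. Their minutes enter therapist time and caregiver time.

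**The case against.** The strongest reply is that the plan already has a rule for this. Item g of the outcomes table leaves out costs that arise only from the evaluation. The recordings are used for JERI and NDBI-Fi rating, and NDBI-Fi change is an outcome in the telerehab arm only, which could explain an observation in that arm only. On this reading nothing is missing.

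The reply fails for the baseline observation. Annex 2 lists it within the proposed telehealth implementation, Visit 5b explains it as a way to see the child's skills at home, and Annex 1 has the FSC, the treatment curriculum, profiled there. The reply may succeed for the final observation, which follows all intervention blocks and sits beside a clinic FSC assessment given to both arms. The documents do not settle that.

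Other parts of the reply stand:
- Table 1 contains no arithmetic error, and no cost formula uses its totals.
- VC observations add no travel.
- Preparation shares the 30-min baseline entry, so the orientation may already be counted there.
- The plan foresees one-way sensitivity analysis, labour and platform costs under item g, and recording of hospital resource use. However, none of these names the VC observations, and the session-charges-only rule would leave them out.

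A reader might also infer that the extra contacts cancel the whole time difference. The documents do not support that. It needs the two midterm recordings to take 30 min each as separate contacts, and neither is stated. A recording might also be made within a VC session already counted, since each session includes a 10-minute play activity; it would then add nothing.

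**Conclusion.** The concern holds for the equal-cost assumption, which Annex 1 contradicts. Using stated durations only, the uncounted telerehab time is 60 min per child, or 50% of the implied 120-min difference, if both observations are programme activity. It is 30 min (25%) if only the baseline one is, which is the part the documents support best. It would be zero if both were evaluation-only, but Annex 2 speaks against that for the baseline observation. The effect of the midterm recordings is unknown.

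The direction is clear: the omission favours telerehab. Whether it could change the cost-saving conclusion cannot be judged, because the documents give no charge or unit cost for these contacts. The percentages treat the 30-min entries as comparable with Table 1 totals that include administration; Annex 1 does not say whether they include it.

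**What to change.** 1. Limit the equal-cost assumption, in both Comparator – Standard Care and Health sector cost, to visits that are identical in the two columns of Annex 1.
2. Add the baseline VC observation, with its preparation, to the telerehab arm's visit count, therapist time and caregiver time, and cost it. State whether the equipment orientation falls inside that 30-min entry, so that it is counted once.
3. Classify the final VC observation as programme or evaluation activity under the item g exclusion, before the cost data are analysed. Cost it if programme, and run the other classification as a one-way sensitivity analysis.
4. Reconcile the midterm VC recordings in the Data collection paragraph with Annex 1: whether they occur, whether they fall inside counted sessions, and how long they take.

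Table 1 can stay as the therapy-time table, with a row added for the telerehab-only contacts. The cost is mainly wording, one or two table rows and a unit cost for the VC observation; the two Annex 1 contacts are already scheduled. The drawback is that the telerehab time and cost comparison becomes slightly less favourable.
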